***Data Collection:***

The following de-identified demographic and clinical data will be collected.

- i. Age
- ii. Sex
- iii. Weight
- iv. Admitting diagnosis and possible site of infection
- v. Blood culture results
- vi. Co-morbidities, including diabetes, hypertension, cardiac failure, COPD, malignancy
- vii. Requirement for mechanical ventilation (Y/N).
- viii. Use of vasopressor agents (Y/N). The hourly dosage of vasopressors will be recorded as the norepinephrine equivalent dosage. [70,71]
- ix. Duration of vasopressor use
- x. Time to vasopressor independence from start of active drug/placebo
- xi. Daily urine output (for first 4 days)

xii. Fluid balance after 24 and 72 hours

xiii. Presence of acute kidney injury (AKI). Presence of AKI: Acute kidney injury (AKI) will be defined using the KDIGO criteria; namely, an increase of the s-creatinine > 0.3 mg/dl or a level > 1.5 times the baseline value. [27] If the baseline s-creatinine is not known a value > 1.5 mg/dl will be regarded as diagnostic of AKI.

xiv. Length of ICU and hospital stay

xv. ICU, hospital, and 28-day mortality

xvi. Routine laboratory data for 4 days including:

a. serum creatinine

b. white cell count (WBC)

c. platelet count

d. total bilirubin

e. PaO2/FiO2 ratio

f. Procalcitonin (PCT) – on days 1 and 4

g. lactate level

h. urine oxalate level (day 4)

xvii. HostDx Sepsis genetic testing (day 1) if consent is provided for additional sub-study.

xviii. The patients' admission APACHE II and APACHE IV scores will be recorded. The APACHE IV score allows calculation of the predicted hospital mortality and predicted ICU length of stay (LOS).

ix. The daily SOFA (Sepsis-related Organ Failure Assessment) score will be recorded for the first 4 treatment days.

The APACHE II score (incrementing score of 0-71) and APACHE IV score (incrementing score 0-286) are standardized measures of disease severity that are used to predict hospital mortality and ICU LOS.

[72,73] The SOFA score was designed to sequentially assess the severity of organ dysfunction in patients who are critically ill from sepsis (incrementing score 0-24). [74]. The SOFA scores is calculated 24 hours

after admission to the ICU and daily thereafter. SOFA scores that increase by about 30 percent are associated with a mortality of at least 50 percent.[75]

Data will be collected in the attached Excel spreadsheet (Appendix A – Sepsis Data spreadsheet). No personal identifiers will be recorded on the spreadsheet. We will not be recording names, dates of birth, social security or EMR numbers or any other HPI data in the data collection spreadsheet. Each record will be assigned a unique study ID number (subject ID key). A separate password protected spreadsheet will have a list of subject ID number and the corresponding medical record numbers (Subject ID Key data sheet). This spreadsheet will only be accessible to the principle investigator and sub-PI. The pharmacist will have a copy of the “Research Randomization and Dispensing Log” with an additional field which will include the randomization code to active vitamin protocol or placebo. Only the pharmacist will have access to the “Research Randomization and Dispensing Log” until after the study is completed, when it will be made available to the principle investigator and sub-PI.

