***Secondary end-points***

- iii. 28-day mortality
- iv. Hospital mortality
- v. PCT clearance (PCT-c) calculated using the following formula: initial PCT minus PCT at 96 hours, divided by the initial PCT multiplied by 100. [67,68]
- vi. ICU mortality
- vii. ICU length of stay (LOS) and ICU free days. ICU free days is calculated as the number of days alive and out of the ICU to day 28
- viii. Hospital LOS

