## **Vitamin C, Hydrocortisone and Thiamine dosing protocol and randomization**

### ***Medication dosing.***

Based on published clinical data, vitamin C pharmacokinetic modeling, the package insert as well as the preliminary study by Marik et al, Vitamin C will be administered as an intravenous dose of 6gm per day divided in 4 equal doses. [22-24,34-37] This dosage is reported to be devoid of any complications or side effects. Hydrocortisone will be dosed according to the consensus guidelines of the American College of Critical Care Medicine.[52] Thiamine will be administered according to current recommendations in a dose of 200mg q 12 hourly. [69]

This is a double-blind placebo controlled study. Only the dispensing pharmacist will be aware of the treatment allocation. Patients will be randomized to receive either vitamin C/hydrocortisone/thiamine or triple placebo using a random number table provided to the dispensing pharmacists. Each patient will be allocated a unique subject ID which will be linked to the randomization sequence. Only the dispensing pharmacists will have a record of the subject ID and randomization sequence. The vitamin C, vitamin C-placebo, hydrocortisone, hydrocortisone-placebo, thiamine, and thiamine-placebo will be formulated as follows:

***Vitamin C:*** Vitamin C is provided by the manufacturer as a 50 ml vial at a concentration of 500mg/ml. Three (3) ml of vitamin C will be placed in a 50 ml bag of Normal Saline (1500 mg vitamin C in 50ml bag) which will then be infused over 30 minutes (100mL/hr). The bag will be labeled by the pharmacy as “Vitamin C 1.5g or Placebo”. The dosing schedule is 1500mg every 6 hours for 4 days (or discontinued earlier if discharged from the ICU).

Once the vial is open, it is only stable for 6 hours. The resulting product is given 12 hour stability. When first ordered, 2 doses are made then and sent to the nurse. For next 12 hours, they will wait until 1 hour prior to make the next batch.

Vitamin C placebo will consist of an identical bag of 50mL normal saline (but with no vitamin C) and will be labeled “Vitamin C or Placebo”. Placebo will be infused over 30 minutes as per the infusion instructions of the active vitamin.

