**Power Calculation:**

Based on the results of the preliminary study of Marik et al we project that the combination of hydrocortisone, vitamin C and thiamine could reduce time to vasopressor discontinuation from 54 (+/- 30 hours) versus 30 hours. For the additional primary outcome we projected a greater change of SOFA score of 4 (+/- 3) versus 2. Assuming a type 1 error of 5% (alpha of 0.05) and a power of 80% (the ability to detect a difference between two groups when a difference exists) would require a sample size of 94 patients. To account for dropouts and patients not requiring vasopressor therapy we will therefore aim for a sample size of 140 patients.

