***Data analysis:***

Summary statistics will be used to describe the clinical data and presented as mean  $\pm$  SD, median with interquartile range (IQR) or percentages as appropriate. Chi squared analysis with Fisher’s exact test (when appropriate) and Student’s t test (Mann Whiney U test for non- normal distributions) were used to compare data between the active treatment group and the placebo group with statistical significance declared for probability values of 0.05 or less.

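### Mortality is compared only by unadjusted tests although a baseline APACHE score is collected; a pre-specified severity-adjusted analysis would usually raise power, by an amount that depends on how well the score predicts death.

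*Protocol*

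**What the plan says.** Item xviii of the Protocol's Data Collection section says that the "admission APACHE II and APACHE IV scores will be recorded. The APACHE IV score allows calculation of the predicted hospital mortality". Under Secondary end-points the Protocol lists "28-day mortality", followed by hospital and ICU mortality.

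For categorical outcomes the Data analysis section names "Chi squared analysis with Fisher’s exact test (when appropriate"), and for continuous outcomes a t test or Mann-Whitney test. These are "used to compare data between the active treatment group and the placebo group with statistical significance declared for probability values of 0.05 or less". The SAP repeats this paragraph. No covariate appears in either document.

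On allocation, the Protocol says only that patients are randomised "using a random number table provided to the dispensing pharmacists". It does not mention stratification by severity.

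The Power Calculation section concerns vasopressor time ("reduce time to vasopressor discontinuation from 54 (+/- 30 hours) versus 30 hours") and delta SOFA. It gives no effect size or power for mortality.

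**The concern.** The plan collects a score that it describes as a basis for predicting hospital death, then leaves it out of the comparison of deaths. Reduced mortality is part of the hypothesis in the Background, alongside less organ failure, and three mortality end-points will each be tested at 0.05. With 140 patients, the unadjusted test has low to moderate power for most effects that fall short of the preliminary study's. A strong baseline predictor could recover some of that power without enrolling anyone else. If the choice is left until the data are unblinded, the adjusted and unadjusted results can differ and there is no stated rule for which one leads.

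**Working it through.** **Plan's own figure.** There is none for mortality. The 94 in the Power Calculation section belongs to the two primary end-points. From the stated inputs, n per arm = 2(1.960 + 0.842)² × (SD/difference)². Delta SOFA gives 15.70 × (3/2)² = 35.3, so 36 per arm or 72 in all. Vasopressor time gives 15.70 × (30/24)² = 24.5, so 25 per arm or 50 in all. The 94 is therefore not recovered as written. That is a separate matter, and only the target of 140 enters below.

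**Inputs from the documents.**
- Target sample size 140; significance level 0.05.
- Background mortality of about 25% (sepsis) and as high as 45% (septic shock).
- Preliminary-study hospital mortality of 40.4% (19/47) versus 8.5% (4/47).

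**Assumptions.**
- 1:1 allocation (70 per arm) and two-sided testing.
- Control mortality of 25 to 45%, with absolute reductions of 10 to 20 points.
- AUC of the score for death of 0.65 to 0.80, with 0.85 to 0.88 as an extreme.

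**Step 1: unadjusted power.** Power = Φ[(d − 1.96 × SE0)/SE1], where d = p1 − p2, SE0 = √(2p̄(1 − p̄)/70) and SE1 = √((p1(1 − p1) + p2(1 − p2))/70).
- 25% v 12.5%: SE0 = 0.0660, SE1 = 0.0651; Φ[(0.125 − 0.1293)/0.0651] = Φ(−0.066) = 47%.
- 40% v 20%: SE0 = 0.0775, SE1 = 0.0756; Φ[(0.200 − 0.1518)/0.0756] = Φ(0.637) = 74%.
- 40.4% v 8.5%: SE0 = 0.0727, SE1 = 0.0675; Φ[(0.319 − 0.1424)/0.0675] = Φ(2.62) = 99.6%.

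**Step 2: adjusted power, by simulation.** There were 6,000 trials per scenario, with 70 per arm. Each trial was analysed by logistic regression on arm plus one normally distributed risk score and a likelihood-ratio test. The gain is the adjusted power minus the chi-square power in the same simulated trials, in percentage points.

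| Mortality, control v active | Chi-square power (formula) | Gain, AUC 0.65 | Gain, AUC 0.70 | Gain, AUC 0.75 | Gain, AUC 0.80 |
|---|---|---|---|---|---|
| 25% v 15% | 31% | 1.9 | 2.5 | 5.0 | 6.8 |
| 25% v 12.5% | 47% | 2.1 | 4.4 | 5.6 | 9.8 |
| 25% v 10% | 65% | 2.9 | 4.7 | 6.3 | 9.5 |
| 40% v 30% | 24% | 2.0 | 3.2 | 4.9 | 7.0 |
| 40% v 25% | 47% | 3.0 | 5.2 | 8.1 | 11.4 |
| 40% v 20% | 74% | 2.9 | 4.7 | 7.1 | 9.6 |
| 45% v 25% | 70% | 3.5 | 4.9 | 8.6 | 13.0 |
| 40.4% v 8.5% | 99.6% | 0.2 | 0.1 | 0.2 | 0.4 |

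Leaving out the last row, the gain is 2 to 5 points at AUC 0.65 to 0.70 and 5 to 13 points at AUC 0.75 to 0.80. With a Wald test the ranges are 0 to 4 and 3 to 12. At AUC 0.85 to 0.88 the likelihood-ratio gain is 10 to 23. The simulation error of one power estimate is at most √(0.25/6000) = 0.6 points.

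**Step 3: type I error.** With equal mortality of 25% or 40% in both arms, rejection was 5.0 to 5.7% (likelihood ratio) and 4.5 to 5.2% (Wald).

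**Step 4: which effect measure.** At 40% v 20% the crude odds ratio is (0.20/0.80)/(0.40/0.60) = 0.375. The covariate-adjusted odds ratio at AUC 0.80 is about 0.27. These are different quantities, so the adjusted odds ratio should not replace the crude contrast. A standardised risk difference from the same model targets the marginal contrast. It was simulated separately (3,000 trials per setting):
- 25% v 12.5%: power rose from 47 to 53% at AUC 0.74 and from 49 to 57% at AUC 0.80.
- 45% v 25%: power rose from 71 to 77% and from 71 to 82%.
- No effect (30% in both arms): rejection was 5.0% and 4.8%.

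**Step 5: can the model be supported?** Expected deaths run from 70 × (0.25 + 0.10) = 24.5 to 70 × (0.45 + 0.25) = 49. For a model with arm and one covariate, that is at least 12 deaths per coefficient.

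**The case against.** The strongest reply is that nothing here is wrong. Under randomisation the unadjusted test is valid, and chance imbalance in severity is already covered by its error rate. Mortality is secondary, and the trial claims no power for it. This stands, and it makes the point an improvement and not a correction.

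Second, the gain rests on inputs that the documents do not give. At the only mortality contrast between treated and control patients that they report, there is almost nothing to gain. This also stands. That contrast comes from a retrospective before-after study with 47 patients per group, however, and the plan itself is more cautious than that study on vasopressor time: it projects 30 hours on active treatment, where the study found 18.3. Smaller mortality effects are therefore worth considering.

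Third, a reader might infer that adjustment is free because predicted mortality is already on file for everyone. The documents do not support this. They say that admission scores will be recorded and that predicted mortality can be calculated from APACHE IV. They set no pre-dose window and give no rule for missing scores. The same section times the SOFA calculation at 24 hours after ICU admission, so pre-dose scoring cannot be taken for granted.

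Fourth, APACHE IV is described as predicting hospital mortality. Its discrimination for 28-day and ICU mortality may differ, and nothing in the documents shows that it is equal.

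**Conclusion.** The point holds as a suggestion to gain efficiency. The plan leaves a baseline severity score out of all three mortality comparisons, and using it would usually raise power with type I error near 5%. Under the assumptions listed, the gain is about 2 to 5 points at AUC 0.65 to 0.70 and about 5 to 13 points at AUC 0.75 to 0.80. It is near zero at 40.4% v 8.5%. The AUC, the mortality effect and 1:1 allocation are all assumed.

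Three stronger readings are not supported. One is that the plan forfeits a fixed amount of power: any single figure depends on an AUC and an effect that the documents do not state. Another is that the mortality comparison is biased for want of adjustment: it is not. The third is that possible imbalance in vasopressor use strengthens the case. The documents give no expected proportion on vasopressors, they are silent on blocking and stratification, and a model with APACHE alone contains no vasopressor term.

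**What to change.** Before unblinding, add to the Data analysis section of the SAP:
- Each mortality end-point (28-day, hospital, ICU) is analysed by logistic regression on arm plus the baseline APACHE IV score, or the logit of its predicted hospital mortality. Name one of the two.
- The result is reported as a standardised risk difference with 95% CI. Chi-square/Fisher is kept as the unadjusted supportive result.
- The score uses only values from before the first dose of study treatment.
- A simple rule is stated for patients whose score is missing.

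The cost is a short SAP addition, a little more analysis work, and possibly some re-scoring from pre-dose values. No additional patients are needed.

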#### ***Inclusion Criteria:***

- i. Diagnosis of sepsis or septic shock within 12 hours of admission to the ICU
- ii. Informed consent as dictated by IRB and local practice.
- iii. Compliance with the 3 hour sepsis bundle
  - 30ml/kg of intravenous crystalloid fluid (e.g.: sodium chloride 0.9%) for lactic acid  $>4$  and/or systolic blood pressure  $<90$ mmHg / mean arterial pressure  $<65$ mmHg
  - Lactic acid level drawn
  - Broad spectrum antibiotics given after obtaining blood cultures

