#### ***Exclusion criteria:***

- i. Age  $< 18$  years
- ii. Pregnant

- iii. DNR/DNI with limitations of care on admission
- iv. Patients with terminal end stage disease (i.e. stage IV cancer, end stage heart failure) that are unlikely to survive to hospital discharge
- v. Patients with a primary admitting diagnosis of an acute cerebral vascular event, acute coronary syndrome, active gastrointestinal bleeding, burn or trauma [64-66]
- vi. Requirement for immediate surgery [64-66]
- vii. Patients with HIV and a CD4 < 50 mm^2 [64-66]
- viii. Patients with known glucose-6 phosphate dehydrogenase (G-6PD) deficiency.[39]
- ix. Patients with sepsis/septic shock transferred from another hospital
- x. Patients with features of sepsis/septic shock > 24 hours after admission

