**Study end-points:**

***Primary end-point***

- i. Time to vasopressor independence. Defined as the time from starting the active treatment/placebo to discontinuation of all pressors
- ii. Delta SOFA score, defined as the initial SOFA score minus the day 4 SOFA score

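### Delta SOFA, a primary end-point, has an undefined initial score and two unreconciled clocks, so its baseline could be taken after the first study dose

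*Protocol*

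**What the plan says.** Protocol, Primary end-point: "Delta SOFA score, defined as the initial SOFA score minus the day 4 SOFA score". The SAP repeats this definition and adds no timing. Neither document defines *initial*, gives an hour for *day 4*, or says whether a score is a snapshot or the worst value of a day.

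Timing appears only in the protocol's Data Collection section, in two places:

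- The last numbered item: the daily "score will be recorded for the first 4 treatment days". This links SOFA to treatment by day. It gives no hour and does not require a score before the first dose.
- The descriptive text after the list: "The SOFA scores is calculated 24 hours" "after admission to the ICU and daily thereafter". This is the only hour given for SOFA, and it is counted from ICU admission.

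The other primary end-point is timed explicitly from the start of study treatment. On entry, the Inclusion Criteria require "Diagnosis of sepsis or septic shock within 12 hours of admission to the ICU". No time from ICU admission to first dose is stated. The dosing section has vitamin C and hydrocortisone given every 6 hours.

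**The concern.** A change score measures treatment effect cleanly only if its starting value is fixed before treatment can act. If the 24-hour sentence is followed and the first dose comes earlier, the starting value is itself affected by treatment. Any benefit present by then lowers the active arm's initial score and is subtracted from its delta, which biases the comparison toward no effect. An early worsening that resolves by day 4 would do the reverse.

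An early effect is plausible on the protocol's own account: in the preliminary before-after study described in the Background, treated patients came off vasopressors a mean of 18.3 hours after starting treatment. Whether that moves SOFA depends on its components, which the documents do not list.

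Even without bias, two abstractors could each follow the protocol and score different days.

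**Working it through.** **1. The clocks side by side.** The treatment-day item gives days 1 to 4 with no hour. The descriptive sentence gives ICU hours 24, 48, 72 and 96. With six-hourly dosing, an assumed first dose at ICU hour 6 puts three doses (hours 6, 12, 18) before a 24-hour score. An assumed first dose at hour 12 puts two before it (hours 12, 18). If the first dose comes after hour 24, that score is pre-dose and the baseline problem does not arise.

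**2. The plan's own figure.** Inputs from Power Calculation: SOFA change 4 versus 2, SD 3; vasopressor time 54 versus 30 hours, SD 30; alpha 0.05; power 80%. Two-sided testing and equal arms are my assumptions. Per arm, n = 2(1.960 + 0.842)² SD²/difference².

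- SOFA: 2 × 7.849 × 9/4 = 35.3, so 36 per arm and 72 in total (74 with the t distribution).
- Vasopressor time: 2 × 7.849 × 900/576 = 24.5, so 25 per arm and 50 in total (52 with t).

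Neither gives the stated 94. That is a separate matter, and nothing below depends on how 94 was derived. I use 94 and 140 only as the stated sizes.

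**3. Power if part of the effect is lost.** Two-sample t test, noncentrality = difference/(3√(2/n)). With n = 70 per arm the standard error is 0.507; with n = 47 it is 0.619. The share lost is assumed.

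| Share lost | Difference | Power, N = 140 | Power, N = 94 |
|---|---|---|---|
| 0 | 2.0 | 97.5% | 89.2% |
| 10% | 1.8 | 94.1% | 82.1% |
| 25% | 1.5 | 83.6% | 66.9% |
| 30% | 1.4 | 78.3% | 61.0% |

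N = 94 is the pessimistic column: part of the allowance from 94 to 140 is for patients not on vasopressors, who still have SOFA scores.

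**4. Both scores on the ICU-admission clock.** Assume the 2-point effect accrues linearly over the 96 hours after a first dose given at ICU hour h, with h at most 24. The share present at ICU hour 24 is (24 − h)/96, and at hour 96 it is (96 − h)/96. The difference is 72/96 = 75%, so 25% is lost whatever h is. Of that, (24 − h)/96 comes from the post-dose baseline and h/96 from a day-4 score that falls less than 96 hours after the first dose. This is the 25% row.

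**5. The opposite direction.** Assume the active arm is 1 point worse at a post-dose baseline and equal to placebo at day 4. The difference in delta is then 1.0 point with no day-4 effect. The test declares a difference about 50% of the time at N = 140 and 36% at N = 94.

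**6. Baseline adjustment.** Take 3 as the SD of change and assume equal variances at both times and correlation rho between them. The ANCOVA standard error is √((1 + rho)/2) times that of the change score. The unadjusted 95% CI half-width at N = 140 is 1.00 point.

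- rho 0.7: ratio 0.922, half-width 0.92.
- rho 0.5: ratio 0.866, half-width 0.87.
- rho 0.3: ratio 0.806, half-width 0.81.

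**The case against.** The 24-hour sentence sits among general remarks on what APACHE and SOFA measure, just before a prognostic comment. It may be background and not an instruction. If so, what remains is an undefined initial score, not a demonstrated post-dose baseline. This stands, and it is why the bias is stated conditionally. It does not remove the gap, because the treatment-day item does not require a pre-dose score either.

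A reader might infer that day 4 has no anchor at all. That goes too far: the collection item ties SOFA to treatment days. What is missing is an hour, and a link from that item to the end-point definition.

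The protocol also refers to an attached data spreadsheet, Appendix A, which is not among the documents reviewed. Timing could be specified there, so the finding is limited to the text supplied.

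On size, the 4-versus-2 projection may have used the same SOFA timing, in which case there is no further loss against the plan. At N = 140 the 10% and 25% illustrations both stay above the planned 80%. Both remarks stand.

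Finally, an unadjusted t test on delta SOFA is valid under randomisation. ANCOVA is a gain in precision, and its amount depends on an assumed rho.

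**Conclusion.** The point holds as a definitional gap in a primary end-point and is worth fixing. *Initial* is undefined, neither score has an hour relative to first dose, and the only hour in the protocol permits a post-dose baseline. Bias requires that the 24-hour sentence is followed, that dosing starts before that score, and that treatment has already changed SOFA by then. None of these can be confirmed from the documents, and the size cannot be derived from them. On the illustrations, the loss is modest at 140 patients: power falls below 80% only when somewhere between 25% and 30% of the effect is lost. At 94 it would matter sooner.

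Two stronger readings are not supported. A reader might infer that the error can only be conservative. That assumes any early effect is benefit; step 5 shows that a transient early worsening could produce a spurious advantage. A reader might also infer that blinding reduces mixed scoring to mere noise. The protocol calls the trial double-blind and limits knowledge of allocation to the dispensing pharmacist, but it does not say who scores SOFA, and research pharmacists belong to the team with access to the data. Blinded scoring is likely but not stated.

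**What to change.** Before unblinding:

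1. Reconcile the two Data Collection sentences and put one rule in both protocol and SAP. For example: initial SOFA uses, for each component, the last value in the 24 hours before first study dose; day-4 SOFA uses the last value from 72 to 96 hours after first study dose.
2. Prespecify how a missing pre-dose component is filled, using neither arm nor post-dose data. The pooled mean of observed pre-dose values for that component would serve, with a sensitivity analysis in patients with complete pre-dose scores.
3. Prespecify what is done for patients who die or leave the ICU before the day-4 window: the value or ranking that a death receives, whether ward values count, and a sensitivity analysis to the choice.
4. With that pre-dose baseline, replace the unadjusted t test by ANCOVA of day-4 SOFA on arm and initial SOFA, reporting the adjusted difference and 95% CI. Apart from sign, the arm effect equals that for delta SOFA adjusted for initial SOFA, so the end-point is unchanged. Do not adjust for a post-dose score, which would remove treatment effect.

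Cost: a definition, a reconciled sentence, a regression and some extra abstraction. The drug-start time is already needed for "Time to vasopressor independence from start of active drug/placebo". Because the Exclusion criteria bar "Patients with sepsis/septic shock transferred from another hospital", earlier values should be in the same hospital's record. The real downside is that the protocol lists "Routine laboratory data for 4 days including" several tests but no pre-dose draw, so some components may be missing. Abstraction must be finished before the subject ID key is destroyed, as Data Safety & storage provides, since values could not easily be recovered afterwards.
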